2.2. Experimental Design: The study design of Aim 2 is the same as Aim 1 (see **Table 2**). We will measure the following biomarkers from reserved serum and urine samples at the baseline, 3, and 6 month visits. Activity of the Nlrp3 inflammasome will be measured via: serum high sensitivity CRP, Xanthine Oxidase

activity level, Nlrp3, Interleukins 1 β and 18, and urine Nlrp3 and IL-18. Renal injury biomarkers will be measured from serum NGAL, urine NGAL, NAG, KIM-1, and ET-1.

2.3. Statistical Analysis: We will report means/medians and standard deviations (SD)/interquartile range (IQR) for all continuous measures. Similar analyses will be used for Specific Aim 2 as Specific Aim 1. All sample size calculations were performed with nQuery Advisor v.7.0.

STUDY INTERVENTION ADMINISTRATION

The proposed intervention uses a study drug (Allopurinol) and concomitant therapy (Candesartan) that are available as generic. The PI is proposing to study the effects of Allopurinol under FDA-approved indications, which is approved for use in children and adults for the reduction of high uric acid levels. Candesartan is approved for use in children and adults for the reduction of high blood pressure. The concomitant therapy, Candesartan, is required in this protocol to reduce drug-drug interactions with Allopurinol. The medications Lisinopril, Enalapril, and Benazepril are commonly prescribed for hypertension but increase the risk of moderate to severe adverse reactions when used concomitantly with Allopurinol. Losartan is also a blood pressure lowering medication that uniquely lowers uric acid levels which could affect the results of the trial, but does not interact with Allopurinol so will be converted for a different and specific reason. Any participant in the trial who is prescribed Lisinopril, Enalapril, Benazepril, or Losartan at the time of randomization will be converted to a similar or same class of blood pressure lowering medication, Candesartan, which does not interact with Allopurinol or lower uric acid levels. Approximately 1/4 of participants in this trial will qualify for the Candesartan conversion. Candesartan will be supplied by the investigational pharmacy at no cost to participants. Allopurinol will also be supplied by the investigational pharmacy to the treatment group participants.

[figure not shown]
Recruitment and pre-trial medication adjustments:

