In the case of Candesartan conversion, the PI along with consultation from the participant's primary nephrologist will prescribe the starting dose of Candesartan. The PI or research coordinator will instruct the participant to STOP Losartan/Lisinopril/Benazepril/Enalapril and START Candesartan on a specific date scheduled 4 weeks before their next SOC visit. The research coordinator or PI will confirm the start/stop date with the participant by phone within 7 days, and if unable to reach the participant or his/her guardian, the Candesartan will NOT be mailed to the participant by the investigational pharmacy. The participant's BP will be checked at their next SOC visit as part of routine care, and their primary nephrologist will make adjustments to the medication as necessary to achieve adequate BP control. If a participant decreases or remains in the same stage of hypertension (as defined by national pediatric BP guidelines) as before the Candesartan conversion (for example, remains in Stage 1 hypertension pre- and post-Candesartan, or moves from Stage 1 to normal pre- and post-), then the participant may continue in the trial. If, however, the participant increases in hypertension stage pre- and post-Candesartan conversion (for example, normal to Stage 1 hypertension pre- and post-) the primary nephrologist will either adjust the Candesartan dose or decide to withdraw the participant from the trial and revert back to the prior medication as they deem necessary. Similarly, if the BP is determined to be too low, the dose will be adjusted or discontinued by the primary nephrologist. Signs and symptoms of low BP will be reviewed with participants prior to the conversion, and participants will be

encouraged to report any symptoms once they are converted. Participants who experience side effects, or those that are withdrawn from the study due to Candesartan conversion will be reported to the PI/research coordinator and Independent Monitor. The Data and Safety Monitoring Plan documents will review this in more detail.

Figure 1. Washout and Medication Conversion Decision Tree

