This randomized controlled trial aims to test the hypotheses that treatment of hyperuricemia with a xanthine oxidase inhibitor (Allopurinol) reduces the rate of decline of kidney function in chronic kidney disease, and markers of renal injury and inflammation. The Data and Safety Monitoring Plan (DSMP) is outlined below. During this study, all data collected will be kept confidential in an encrypted database using identification codes. Only approved research team members will have access to the database. The study staff will review all data collection forms on an ongoing basis for data completeness and accuracy as well as protocol compliance. Reviews of subject accrual, including compliance with protocol enrollment criteria and adherence data, will be performed by the PI and study staff on a monthly basis.

Data on adherence to the treatment protocol will be collected on an ongoing basis by research staff and reviewed quarterly by the PI. Adherence of participants will be evaluated by performing pill counts at study visits and by a validated visual analogue scale of adherence (patient self-report) at the end of study visit. An intention to treat protocol is applied to this study. However, if adherence falls below a rate of 75% which might inhibit the ability of the study to test its primary hypotheses, the study investigators and statistician will convene to discuss methods for improving adherence.

The PI will designate an Independent Monitor to perform an independent review of ongoing study progress and safety. The Independent Monitor will not be a part of the key research personnel, and will be qualified to review the patient safety data. Progress reports, including patient recruitment, retention/attrition of the study as a whole as well as retention of subjects undergoing washout or conversion therapy to study initiation, and adverse events (AE), will be provided to the Independent Monitor every 6 months. The reports will be generated only from aggregate for the entire study population. A closed safety report with masked group assignment will be generated for the Independent Monitor by an unmasked member of the study team (research coordinator).

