An Annual Report will also be compiled and will include a list and summary of AEs. In addition, the Annual Report will address (1) whether AE rates are consistent with pre-study assumptions; (2) reason for dropouts from the study; (3) whether all participants met entry criteria; (4) whether continuation of the study is justified on the basis that additional data are needed to accomplish the stated aims of the study; and (5) conditions

whereby the study might be terminated prematurely. The Annual Report will be sent to the Independent Monitor and will be forwarded to the IRB.

AE reports and annual summaries will not include identifiable material. Each report will refer only to the subjects' identification code. An AE is any untoward medical occurrence in a subject during participation in the clinical study or with use of the intervention agent being studied. An adverse finding can include a sign, symptom, abnormal assessment (laboratory test value, vital signs, skin reaction or physical exam finding), or any combination of these. A serious adverse event (SAE) is any adverse event that results in one or more of the following outcomes:

- Death
- A life-threatening event
- Inpatient hospitalization or prolongation of existing hospitalization
- A persistent or significant disability/incapacity
- A congenital anomaly or birth defect
- An important medical event based upon appropriate medical judgment

AEs will be labeled according to severity, which is based on their impact on the patient. An AE will be termed "mild" if it does not have a major impact on the patient, "moderate" if it causes the patient some minor inconvenience, and "severe" if it causes a substantial disruption to the patient's well-being. AEs will also be categorized according to the likelihood that they are related to the study intervention and labeled: definitely unrelated, definitely related, probably related, or possibly related to the study intervention. AEs will be reviewed with participants at each study visit.

Occasional 1-10% mild AEs are mild nausea, mild elevation in liver transaminase levels, and are not expected to impact a patient. These risks are considered minimal and will be addressed in the protocol and consent form.

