The rate of moderate AEs is expected to be <1%. The protocol includes measures to reduce the risk of moderate to severe AEs. Moderate AEs include skin reaction, gastrointestinal distress, moderate elevation in liver transaminases. Subjects will be encouraged to report these occurrences at any time during the intervention period by telephone within 24 hours of experiencing an event. Any adverse event rate over 5% in 12 months will be reported to the IRB.

Severe AEs include skin reaction as with development of Stevens-Johnson syndrome, or a significant elevation in liver transaminase levels that require hospitalization, and will be reported immediately to the IRB if this occurs. SAEs that are unanticipated, serious, and possibly related to the study intervention will be reported to the Independent Monitor and IRB in accordance with requirements. The Independent Monitor will be a clinician appointed by the PI who is not involved with the study design or analysis and is not a study investigator.

Unexpected fatal or life-threatening AEs related to the intervention will be reported to the IRB within 7 days. Other serious and unexpected AEs related to the intervention will be reported to the IRB within 15 days. Anticipated or unrelated SAEs will be handled in a less urgent manner but will be reported to the Independent Monitor and IRB. In the annual AE summary, the Independent Monitor Report will state that they have reviewed all AE reports.

The study staff, PI, and Independent Monitor will review the conglomerate adverse event rates every 6 months. Review of AE and SAE reports will also occur on an ongoing basis by the PI and study staff.

This study will be stopped prior to its completion if: (1) the intervention is associated with adverse effects that call into question the safety of the intervention; (2) difficulty in study recruitment or retention will significantly impact the ability to evaluate the study endpoints; (3) any new information becomes available during the trial that necessitates stopping the trial; or (4) other situations occur that might warrant stopping the trial.

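### The safety plan ties relatedness and the 7- and 15-day IRB clocks to an undefined *study intervention*, so the status of the required Candesartan conversion is unclear, and Table 1 schedules no AE evaluation at V1 or for controls

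*Combined protocol and SAP*

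**What the plan says.** **The conversion.** Study Intervention Administration says: "The concomitant therapy, Candesartan, is required in this protocol to reduce drug-drug interactions with Allopurinol". Anyone in the trial taking Lisinopril, Enalapril, Benazepril or Losartan is converted, with no restriction by arm, and "Approximately 1/4 of participants in this trial will qualify for the Candesartan conversion". The investigational pharmacy supplies the drug. The same section opens: "The proposed intervention uses a study drug (Allopurinol) and concomitant therapy (Candesartan) that are available as generic".

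**Safety reporting for the conversion.** The subsection on recruitment and pre-trial medication adjustments covers participants who have side effects, and those "withdrawn from the study due to Candesartan conversion will be reported to the PI/research coordinator and Independent Monitor". It then says: "The Data and Safety Monitoring Plan documents will review this in more detail".

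**The DSMP.** It describes the hypothesis under test as being that "treatment of hyperuricemia with a xanthine oxidase inhibitor (Allopurinol) reduces the rate of decline of kidney function in chronic kidney disease". On causality, "AEs will also be categorized according to the likelihood that they are related to the study intervention". Unexpected fatal or life-threatening events related to the intervention go to the IRB within 7 days, and other serious unexpected related events within 15 days. For the rest, "Anticipated or unrelated SAEs will be handled in a less urgent manner", though that sentence goes on to say they are still reported to the Independent Monitor and the IRB. AEs are to be reviewed at each study visit.

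**AE collection.** Section 1.2 has AEs collected at V1A, V2 and V3. In Table 1, AE evaluation is part of code F, which appears for the treatment group at V1A, V2 and V3 and nowhere in the control row.

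**The concern.** The Candesartan switch happens because of the trial, and it can reach participants who never take trial Allopurinol. Whether a harm from that switch counts as related, and which reporting deadline then applies, depends on a term the plan leaves open. The first stopping criterion, which concerns adverse effects associated with the intervention, uses the same term.

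At stake is the speed and labelling of a report on a serious, unexpected event caused by a protocol-required drug change in a child. The AE schedule adds to this. Table 1 gives no prompt to ask about events at V1, the first study visit after the conversion or washout month, and none for converted controls afterwards.

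**Working it through.** **1. Scale.** The base is the planned sample of 42, allocated 28 to 14 (section 1.3, Table 2). That figure reproduces. With a difference of 3 and SD of 3.5, the noncentrality is 3 / (3.5 × √(1/28 + 1/14)) = 2.62, and the one-sided t-test at 0.05 has exact power of 82.4%, above the stated 80%. Nothing in this point changes it.

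- Converted: 0.25 × 42 = 10.5, so about 10 to 11.
- If conversions follow the 2:1 allocation (assumed): 0.25 × 28 = 7 on Allopurinol and 0.25 × 14 = 3.5, so 3 to 4 controls.

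The quarter is the protocol's own figure, given without derivation. Participants withdrawn during conversion, before randomisation, may fall outside the 42.

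**2. What the intervention covers.** No passage defines the term for safety reporting.

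| Place | Points to |
|---|---|
| Study Intervention Administration, opening sentence | Both drugs |
| Same section, labels given to each drug | Allopurinol as study drug, Candesartan as concomitant therapy |
| DSMP, statement of hypothesis | Allopurinol |
| DSMP, AE definition (intervention agent, singular) | Can be read as Allopurinol only |
| DSMP, causality and 7/15-day rules | Term used, not defined |

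**3. The promised detail.** The DSMP text does not name Candesartan. It mentions conversion only when asking for retention figures for participants undergoing washout or conversion. Its examples of mild, moderate and severe events include no blood-pressure event, although the recruitment subsection foresees blood pressure that is too low after conversion.

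**4. Consequence of each reading, for a serious unexpected reaction to the conversion.**

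- Broad reading: related, so the 7- or 15-day clock applies.
- Narrow reading: unrelated, so it goes to the Monitor and IRB with no time limit.

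The recruitment subsection's own route, to the study team and the Monitor, has no clock, no IRB step and no causality rule.

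**5. When the rules start.** Consent comes before conversion or washout, and the AE definition covers events during participation. But section 1.2 puts the washout before enrolment and Table 1 puts enrolment at V1. The plan does not say whether the run-in counts as participation.

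**6. AE evaluation by visit.**

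| Visit | Treatment (Table 1) | Control (Table 1) | DSMP |
|---|---|---|---|
| V1 | No F | No F | Review |
| V1A | F | No visit | Review (treatment) |
| V2 | F | No F | Review |
| V3 | F | No F | Review |

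The section 1.2 text also omits V1. It names no arm, so the control gap at V2 and V3 comes from Table 1. These passages must be reconciled.

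**The case against.** The strongest reply is that the only sentence saying what the intervention consists of names both drugs, under a heading about administering the study intervention. The DSMP's Allopurinol sentence states the hypothesis; it does not set the scope of safety reporting. A reader might infer that the plan judges causality against Allopurinol alone. The documents do not say so, and the point is limited to an undefined term with two tenable readings.

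A reader might also infer that Candesartan harms would go unreported. That is not supported. AEs are not restricted to one drug, the six-monthly progress reports include AEs for the whole study, conversion side effects go to the Monitor, and unrelated SAEs still reach the Monitor and IRB. AE rates above 5% in 12 months go to the IRB whatever their cause. Severe AEs are to be reported to the IRB immediately, in a sentence not conditioned on relatedness, though its examples are a severe skin reaction and a liver-enzyme rise requiring hospitalisation. Nor can one conclude that the regimen would be presented as safer than it was, because the plan specifies no count or analysis of related events. The documents do not assign the listed events to either drug, so the list cannot be called Allopurinol-specific.

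Finally, the DSMP is described as an outline, the recruitment text refers to DSMP documents in the plural, and the decision-tree figure is not shown. A fuller plan may hold the missing detail.

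All of this stands as a limit on the harm. It does not supply a definition or a clock for conversion events, and it does not remove the mismatch between Table 1 and the DSMP. If a fuller plan exists, the protocol should cite it.

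**Conclusion.** The point holds as a gap in definition plus an inconsistency in AE collection. The protocol requires the conversion in either arm, the expedited clocks rest on an undefined term, and the promised conversion detail is absent from the DSMP text supplied. The exposure is about 10 to 11 of 42 participants; the 3 to 4 controls among them depend on conversions following the allocation ratio. On the narrow reading, any reaction to Candesartan in those controls would be unrelated by construction.

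The consequence is a late or mislabelled report of a serious unexpected event, under one of two readings. An event treated as anticipated takes the slower route under both. No event rate is given, so the expected number of such events cannot be estimated. Sample size, power and alpha are unaffected. The change is worth making because it concerns safety in children and costs little.

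**What to change.** In the DSMP:

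- State that *study intervention* covers Allopurinol, the protocol-required Candesartan conversion and the washout.
- Record causality separately for each of the three.
- Apply the existing 7-day, 15-day and Monitor rules to relation to any of them, from the start of conversion or washout.
- Supply the promised detail on conversion side effects, or cite the document that holds it.
- List events among converted participants in the six-monthly report.

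In section 1.2 and Table 1, add AE evaluation at V1 for both arms, covering the run-in, and at V2 and V3 for controls, so that the schedule agrees with the DSMP.

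The cost is DSMP wording, causality fields on the AE form, a few Table 1 codes and a short listing. It adds no visit or test and changes no treatment rule.
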